7.4.3 Analysis of Exploratory Endpoints

Subgroup analyses by PSA cutoff scores for < 2, 2-4 will be performed.

7.5 Analysis of Safety

7.5.1 Adverse Events

Adverse events will be coded using the Medical Dictionary for Regulatory Activities (MedDRA). The number and percentage of treatment-emergent AEs, SAEs, AEs leading to discontinuation, and AEs related to study drug will be summarized by system organ class, preferred term and treatment group. The number and percentage of TEAEs by severity and relationship to study drug will also be summarized. All AEs will be listed.

7.5.2 Laboratory Assessments

Laboratory variables (biochemistry, hematology, and urinalysis) will be descriptively summarized for Baseline (Visit 2), Week 4, Week 8, and Week 12/EOT and change from Screening to EOT will be summarized by treatment group.

For each hematology and biochemistry laboratory parameter, laboratory test results will be classified as low (L), normal (N), or high (H) according to the laboratory-supplied reference ranges. Shift tables of reference range changes from Screening to Week 12/EOT and most extreme value during the double-blind treatment period by treatment group will be summarized.

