PPBC	Patient Perception of Bladder Condition
PPIUS	Patient Perception of Intensity of Urgency Scale
PR	Pulse Rate
PRO	Patient Reported Outcomes
PTM	Placebo to Match
PTNS	Percutaneous Tibial Nerve Stimulation
PVR	Post-Void Residual Volume
QD	Once Daily
Q _{max}	Maximum urinary flow rate
QoL	Quality of Life
QT	Time interval between QRS complex to end of T wave
QTcF	Fridericia's Correction Formula
SAE	Serious adverse event
SAF	Safety Analysis Set
SAP	Statistical Analysis Plan
SBP	Systolic Blood Pressure
SD	Standard Deviation
SE	Standard Error
SFL	Screen failure log
SOP	Standard Operating Procedure
SPC	Summary of Product Characteristics
SUSAR	Suspected unexpected serious adverse reactions
t _{1/2}	Terminal Elimination Half-Life
TBL	Total bilirubin
TEAE	Treatment Emergent Adverse Event
TMF	Trial Master File
TLF	Tables, Listings and Figures
TS-VAS	Treatment Satisfaction Visual Analog Scale
TUFS	Total Urgency and Frequency Score
ULN	Upper Limit of Normal
US	United States
UTI	Urinary Tract Infection
YM178	Mirabegron/Myrbetriq/Betmiga

Definition of Key Study Terms

Terms	Definition of terms
Adverse Event	An adverse event is any untoward medical occurrence in a subject administered a study drug and which does not necessarily have a causal relationship with this treatment.
Baseline	The baseline value is defined as the last measurement before the first dose of double-blind study drug. For variables based on the electronic diary, the 3 days of the diary recorded prior to the randomization visit will be used to derive these variables at baseline.
Discontinuation	The act of concluding participation, prior to completion of all protocol-required elements, in a trial by an enrolled subject.
End of Study	The time of the last subject's last protocol-defined assessment.
Enrolled	A screened subject who has received the study medication.
Frequency	The complaint of voiding too often during the day.
Incontinence	Any involuntary leakage of urine. For purposes of data analysis specifically for this study, both full void incontinence with or without any urgency as well as partial void incontinence with passed urine in the toilet will be considered as incontinence.
Micturition	Any voluntary micturition (episodes of incontinence only are not included).
Mixed urinary incontinence	The complaint of involuntary leakage associated with urgency and also with exertion, effort, sneezing or coughing.

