Safety analyses will be done on the Safety Analysis Set (SAF), which consists of subjects who received at least one dose of double-blind medication. Treatment emergent adverse events will be coded using the MedDRA dictionary and will be summarized by treatment group. The number and percentage of treatment-emergent AEs, SAEs, AEs leading to discontinuation, and AEs related to study drug will be summarized by system organ class, preferred term and treatment group. Laboratory variables (biochemistry, hematology, and urinalysis) will be descriptively summarized for Baseline (Visit 2), Week 4, Week 8, and Week 12/End of Treatment and change from Screening to End of Treatment will be summarized by treatment group. Vital sign changes will be summarized by treatment group. Categorical changes in vital signs will also be examined. In addition, post-void residual volumes as measured by bladder sonography and Q_{max} will be summarized by change from baseline. Centrally assessed ECGs will also be summarized by treatment group.

Interim analyses:

Not applicable.

V. FLOW CHART AND SCHEDULE OF ASSESSMENTS

Flow Chart

mirabegron 25 mg QD plus tamsulosin hydrochloride 0.4 mg QD	mirabegron 50 mg QD plus tamsulosin hydrochloride 0.4 mg QD
placebo matched to mirabegron 25 mg QD plus tamsulosin hydrochloride 0.4 mg QD	placebo matched to mirabegron 50 mg plus tamsulosin hydrochloride 0.4 mg QD

[figure not shown]

Table 1 Schedule of Assessments

	Screening/ Tamsulosin Hydrochloride Run- In	Treatment Period				Follow-up Phone Call
		2	3	4	5	
Visit	1	2	3	4	5	6
Day	-28	1	28	56	84	114
Week	-4	0	4	8	12	16
Visit Windows	+/- 3 d	—	+/- 7 d	+/- 7 d	+/- 7 d	+/- 3 d
Visit Windows (Study Days) ^a	-31 to -25	—	21 to 35	49 to 63	77 to 91	111-117
Informed Consent	X					
Inclusion/Exclusion Criteria	X	X				
Medical History and OAB History	X					
Demographics	X					
Enter 4-week tamsulosin hydrochloride run-in ^b	X					
Reminder Phone Call ^c		X	X	X	X	
Randomization ^d		X				
Physical Exam	X				X	
Weight and Height	X					
Office Visit Vital Signs (pulse and blood pressure)	X	X	X	X	X	
Serum PSA	X					
Serum chemistry, hematology & urinalysis ^{e, f}	X	X	X	X	X	
12-Lead ECG ^g	X	X	X	X	X	
PVR (Ultrasonography or Bladder Scan)	X	X	X	X	X	
Uroflowmetry (Q _{max}) ^h	X				X	
IPSS	X	X	X	X	X	
Medication History and OAB Medication History ⁱ	X					
Concomitant Medications Assessment	X	X	X	X	X	X
Adverse Event Assessment ^j	X	X	X	X	X	X
Dispense Study Drug	X	X	X	X		
Drug Accountability		X	X	X	X	

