5.8 Total Amount of Blood

Blood samples will be taken for the purposes of hematology, biochemistry and PSA analysis at Screening/tamsulosin hydrochloride run-in (Visit 1), Baseline (Visit 2), Week 4 (Visit 3), Week 8 (Visit 4), and Week 12/End of Treatment (Visit 5). It is anticipated the total amount of blood taken will not exceed 50 mL throughout the duration of the study.

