7 STATISTICAL METHODOLOGY

The statistical analysis will be coordinated by the responsible biostatistician of Astellas. A Statistical Analysis Plan (SAP) will be written to provide details of the analysis, along with specifications for tables, listings and figures to be produced. The SAP will be finalized before database softlock at the latest. Any deviations from the analysis planned in SAP will be justified in the Clinical Study Report (CSR).

Prior to Database Lock, a Final Review of Data and TLFs Meeting will be held to allow a review of the clinical trial data and to verify the data that will be used for analysis set classification. If required, consequences for the statistical analysis will be discussed and documented. A meeting to determine analysis set classifications may also be held prior to database hard lock.

In general, baseline is defined as the last measurement before the first dose of double-blind study drug. For variables based on the electronic diary, the 3 days of the diary recorded prior to Visit 2/Baseline (Week 0) will be used to derive these variables at baseline just as the 3 diary days before each post-baseline visit will be used to derive these variables at these visits.

The End of Treatment (EOT) visit is defined as the last post-baseline visit during the double-blind study period for which data is available. The EOT visit value for diary variables is the average or number of the diary measurements for Week 12, as applicable. If no Week 12 diary data measurements are available, then the last available earlier post-baseline average or number of the diary measurements within a designated visit window will be used (LOCF). Data from the EOT visit will be analyzed to account for subjects prematurely terminating the study and is regarded as the primary visit. The EOT visit will be Week 12/EOT (Visit 5) for subjects who complete the study.

All statistical comparisons will be made using a two-sided test at $\alpha = 0.05$ significance level and confidence intervals (CIs) will be reported with a coverage consistent with this significance level unless specified otherwise.

All efficacy and safety variables will be summarized using descriptive statistics. Continuous variables will be summarized using the descriptive statistics number of non-missing observations (N), mean, standard deviation (SD) or standard error (SE), minimum, median, and maximum unless specified otherwise. Categorical variables will be described using N and percent.

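### Laboratory change and shift tables start from Screening rather than the protocol's own pre-dose baseline, without a stated reason, so some individual shifts are assigned to the wrong period

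*Protocol*

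**What the plan says.** Section 7.5.2 summarizes laboratory variables at Baseline (Visit 2) and at Weeks 4, 8 and 12/EOT. It then states that "change from Screening to EOT will be summarized by treatment group". Its next paragraph plans "Shift tables of reference range changes from Screening to Week 12/EOT and most extreme value during the double-blind treatment period". The safety paragraph of the synopsis has the same rule for change: "change from Screening to End of Treatment will be summarized by treatment group".

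The protocol defines baseline twice. The Definition of Key Study Terms has "The baseline value is defined as the last measurement before the first dose of double-blind study drug". Section 7 has "In general, baseline is defined as the last measurement before the first dose of double-blind study drug", which differs only in its opening qualifier.

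Hematology, biochemistry and urinalysis are scheduled at both Visit 1 and Visit 2 (Table 1; Section 5.4.4, Table 3). Footnote d to Table 1 places randomization after all other Visit 2 procedures, so the Visit 2 sample comes before double-blind dosing.

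**The concern.** The value that Section 7.5.2 labels Baseline is not the value from which change and shifts are measured, and no reason is given. The tables therefore cover the open-label run-in as well as the double-blind period, although they will be read as describing the latter. No laboratory change or shift from Visit 2 is specified anywhere in the protocol.

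Safety and tolerability are the secondary objective. The treatment-emergent adverse event window opens at the first double-blind intake, so the laboratory tables and the adverse event tables would also have different starting points.

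**Working it through.** The plan gives no figure for this point, so there is none to reproduce. The check compares the texts, works through the classification and then gives an illustration under stated assumptions.

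**1. Reference points in the safety section**

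| Variable | Measured at Visits 1 and 2? | Reference for change |
|---|---|---|
| Office vital signs (7.5.3) | Yes | Baseline |
| ECG (7.5.5) | Yes | Baseline |
| PVR (7.5.6) | Yes | Baseline |
| Qmax (7.5.7) | Visit 1 only | Start of run-in, stated as such |
| Laboratory (7.5.2) | Yes | Screening |

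The laboratory variables are the only ones measured at both visits whose change is taken from the earlier visit.

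**2. Interval covered.** In Table 1, Screening is Day -28, Visit 2 is Day 1 and Week 12 is Day 84. The run-in may last 22 to 34 days (footnote b). The tabulated interval is about 16 weeks, of which 4 precede double-blind dosing. For each man:

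(EOT − Screening) = (Visit 2 − Screening) + (EOT − Visit 2).

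The first term on the right is run-in change.

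**3. Classification of men high at EOT**

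| Screening | Visit 2 | EOT | From Screening | From Visit 2 |
|---|---|---|---|---|
| Normal | Normal | High | Shift | Shift |
| Normal | High | High | Shift | No shift |
| High | Normal | High | No shift | Shift |
| High | High | High | No shift | No shift |

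The two rules disagree in rows 2 and 3 only. The difference in total shifts is the row 2 count minus the row 3 count. If Screening and Visit 2 values have the same distribution and the same correlation with EOT, these counts are equal in expectation. The totals then agree and only the individuals differ.

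**4. Illustration.** Assumptions not in the documents: normal values, equal correlation r between all visits, upper limit at 1.96 SD, no drug effect, and run-in drift of 0 or 0.2 SD. Scaling uses the 320 men per arm of Section 3.1. The results come from 1,000,000 simulated men per setting.

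| r | Drift (SD) | Shifts per 320 from Screening / Visit 2 | Screening-based shifts already high at Visit 2 | Visit 2-based shifts not counted from Screening | Wrongly counted / missed per 320 |
|---|---|---|---|---|---|
| 0.5 | 0 | 6.6 / 6.6 | 15% | 15% | 1.0 / 1.0 |
| 0.7 | 0 | 5.3 / 5.3 | 23% | 23% | 1.2 / 1.2 |
| 0.85 | 0 | 4.0 / 3.9 | 32% | 31% | 1.3 / 1.2 |
| 0.5 | 0.2 | 10.7 / 9.9 | 18% | 12% | 1.9 / 1.2 |
| 0.7 | 0.2 | 9.2 / 7.9 | 29% | 17% | 2.6 / 1.4 |
| 0.85 | 0.2 | 7.5 / 5.8 | 39% | 20% | 2.9 / 1.2 |

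For example, at r = 0.5 with no drift, 2.05% of men shift from Screening and 15.0% of those were already high at Visit 2: 320 × 0.0205 × 0.150 = 0.98. The small gap at r = 0.85 with no drift is simulation error. With drift of 0.2 SD, mean change is 0.20 SD from Screening and 0.00 from Visit 2.

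**5. Noise in mean change.** With equal correlations, the SD of change is the same from either visit, so there is no penalty. If correlation instead decays with time (first-order autoregressive, 4-week correlation r), the ratio of SDs over 16 and 12 weeks is √[(1 − r⁴)/(1 − r³)]. For r = 0.7 this is √(0.7599/0.657) = 1.075. For r = 0.9 it is √(0.3439/0.271) = 1.13. The penalty is thus zero under the model of step 4 and about 8% to 13% under the other. The two models are alternatives, and their results should not be added together.

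**6. Between arms.** Allocation happens at Visit 2, after the run-in. The run-in term in step 2 has the same expectation in both arms and drops out of the difference.

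**The case against.** The strongest reply is that this is a deliberate choice. Section 7 opens its definition with a qualifier that leaves room for exceptions, and the laboratory tables name Screening openly. The synopsis and Section 7.5.2 agree on change, and Qmax also uses a run-in-start value. Much of this stands: the text does not give two conflicting instructions, and calling it a contradiction would go too far. It is still an unexplained departure. The key-terms definition carries no qualifier, and Qmax is declared as an exception and has no Visit 2 measurement to use.

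A reader might also infer that the comparison of mirabegron with placebo is biased. The documents do not support that, because the run-in precedes randomization. Nor do they point to a material drug effect during the run-in, since eligible men had already taken the same tamsulosin dose for at least 2 months (inclusion criterion 2). Ordinary within-subject variation is enough to produce the misclassification. Because liver-enzyme eligibility is listed under Visit 1, regression to the mean could also contribute, equally in both arms.

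A reader might further infer that on-treatment shifts are missed in general. Only those of men abnormal at Screening and normal at Visit 2 are missed.

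Finally, individual liver safety does not rest on these tables. Section 6.1 and Appendix 2 work from multiples of the upper limit of normal. Mean change from Visit 2 can also be approximated from the planned visit summaries, though individual shifts cannot.

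**Conclusion.** The point holds as an unexplained departure from the protocol's own baseline, in descriptive safety tables. Followed as written, the plan assigns some run-in shifts to double-blind treatment and hides some shifts that occurred on treatment.

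The direction of each misclassification follows from the definitions alone. The size does not, because the documents give no within-subject correlations and no run-in drift. Under the assumptions shown, the Screening reference wrongly counts about 1 to 3 men and misses about 1 per parameter per 320-man arm. With equal correlations and no drift, these cancel in the expected totals. The loss of precision in mean change ranges from none to about 13%, depending on the correlation model. No systematic bias between arms follows, and efficacy is untouched. The correction is worth making because the better reference value is already collected.

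**What to change.** In Section 7.5.2 and in the safety paragraph of the synopsis, replace Screening by Baseline as the reference, stated as the last value before the first double-blind dose, normally Visit 2. Apply this to change to EOT and to the shift tables, both to Week 12/EOT and to the most extreme double-blind value.

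The reference should be worded as the last pre-dose value, not as Visit 2 with Screening as the fallback. Section 5.4.4 allows one repeat test between Visits 1 and 2. If the Visit 2 value is missing, that repeat, where there is one, is the last pre-dose value.

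Screening-based tables may be kept as a supplement if the whole study period is of interest. The cost is a wording change in two places and the matching table specifications. No new samples or visits are needed.

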7.5.3 Vital Signs

Pulse rate, systolic blood pressure, and diastolic blood pressure will be summarized by treatment group using descriptive statistics (mean, standard deviation, minimum, maximum and median) for baseline value, post-baseline time point values (Week 4, Week 8, and Week 12/EOT), and change from baseline to each post-baseline time points. The average change from baseline to end of treatment for each vital sign variable will be analyzed using the ANCOVA model with treatment group and geographic region as fixed factors and baseline vital sign value as covariate. Results will be summarized separately for office based measurements and HBPM. No p-values will be calculated.

An analysis of change from baseline of vital signs using a Mixed Model Repeated Measures (MMRM) model with geographic region, age group, time (visit), and a time-by-treatment interaction as factors and the baseline values as covariate will serve as another sensitivity analysis. The repeated measures model will present LS means and two-sided 95% CIs for changes from baseline within each treatment group.

Number and percentage of subjects with more than 2/5/10/15/20 mmHg increase from baseline in SBP, more than 2/5/10/15 mmHg increase in DBP or more than 5/10/15 bpm increase from baseline in pulse rate, on 2 consecutive post-baseline visits will be summarized by treatment group. Number and percentage of subjects with vital sign values shifting between JNC-7 defined risk categories will be summarized by treatment group. These categories are listed below:

Category	Systolic BP (mm Hg)	Diastolic BP (mm Hg)
Normal	< 120	<80
Prehypertension	120-139	80-89
Hypertension Stage 1	140-159	90-99
Hypertension Stage 2	\geq 160	\geq 100

Number and percentage of subjects with a PR > 100 bpm at any office visit or by HBPM will be summarized by treatment group separately.

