changes observed for mirabegron 50 mg and tolterodine. Pulse increases were more pronounced in young subjects in comparison to older adults (age 55 years and greater) subjects. Changes in pulse were reversible upon discontinuation of treatment.

An approximate mean increase in 1 mmHg from baseline for SBP/DBP was observed in OAB patients who received mirabegron 50 mg compared with placebo. This magnitude of change was similar for both 12-week and long-term studies, for men and women, and in both the mirabegron and tolterodine treatment groups. TEAE and SAE related to hypertension were similar for mirabegron 50 mg, placebo, and tolterodine in the 12-week studies, and were similar for mirabegron and tolterodine in the long-term study. Blood pressure increases were more pronounced in young subjects in comparison to older adult (age 55 years and greater) subjects. Changes in blood pressure were reversible upon discontinuation of treatment. Please refer to the product insert for expected adverse drug reactions (ADR).

Detailed information on the clinical safety profile for mirabegron can be found in the full prescribing information [Mirabegron US Package Insert, 2015, Myrbetriq Canadian Monograph, March 2015, and EU SmPC, 2015].

According to current package inserts, no dose adjustment is necessary for older adult patients. The pharmacokinetics of mirabegron is not significantly influenced by age. The C_{max} and AUC of mirabegron following multiple oral doses in older adult volunteers (≥ 65 years) were similar to those in younger volunteers (18 to 45 years). Of 5,648 patients who received mirabegron in the phase 2 and 3 studies, 2,029 (35.9%) were 65 years of age or older, and 557 (9.9%) were 75 years of age or older. No overall differences in safety or effectiveness were observed between patients younger than 65 years of age and those 65 years of age or older in the studies [Mirabegron US Package Insert, 2015 and Myrbetriq Canadian Monograph, March 2015, EU SmPC, 2015].

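### The main vital-sign ANCOVA omits age group while its sensitivity MMRM includes it, so the two analyses differ in covariates as well as in missing-data handling, and no reason is given

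*Protocol*

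**What the plan says.** Section 7.5.3 of the protocol fixes two linear models for systolic pressure, diastolic pressure and pulse rate.

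- **Main model**, for change to end of treatment: an "ANCOVA model with treatment group and geographic region as fixed factors and baseline vital sign value as covariate". Section 7.10 makes end of treatment an LOCF value for vital signs. Section 7.5.3 adds: "No p-values will be calculated".
- **Repeated-measures model**: an MMRM with "geographic region, age group, time (visit), and a time-by-treatment interaction as factors and the baseline values as covariate", which "will serve as another sensitivity analysis". The only output named for it is LS means with 95% CIs for change within each treatment group.

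Age group is also a factor in the primary efficacy ANCOVA (7.4.1.1), the micturition MMRM (7.4.1.2) and the patient-reported-outcome MMRM (7.4.2).

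On age, section 1.3.1 says: "Blood pressure increases were more pronounced in young subjects in comparison to older adult (age 55 years and greater) subjects". It says the same of pulse: "Pulse increases were more pronounced in young subjects in comparison to older adults (age 55 years and greater) subjects". On the size of the drug effect it says: "An approximate mean increase in 1 mmHg from baseline for SBP/DBP was observed in OAB patients who received mirabegron 50 mg compared with placebo".

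**The concern.** A sensitivity analysis is read by comparing it with the main analysis. Here the intended contrast is LOCF at end of treatment against a repeated-measures model without LOCF. Because the covariate list changes as well, a reader who sees different numbers cannot tell which change produced them.

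The term left out is the one that section 1.3.1 connects with these outcomes. Safety is the secondary objective (2.1), and blood pressure and pulse rate are listed as adverse events of special interest (5.4.3.2). Effects near 1 mmHg are in question, so even a small artificial shift between tables can distract.

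**Working it through.** **Plan's own figures.** The protocol gives no SD, sample size or precision for vital signs. Its only sample-size figure concerns micturitions (7.1), and it reproduces: 2 × (1.960 + 0.842)² × 2.7² / 0.65² gives 271 per group against 272 stated, and 272 gives 80% power. I use 272 per group only as a convenient n. Every vital-sign input below is an assumption.

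**1. Bias.** Allocation is 1:1, stratified by region only (4.5), and region is in the ANCOVA. A linear model with or without another baseline factor therefore targets the same average treatment difference. I checked this by simulating 2,000 trials of 544 men with residual SD 10 mmHg:

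| Scenario | True average | Estimate without / with age | SE without / with age | Mean absolute difference between estimates |
|---|---|---|---|---|
| Effect 3.0 young, 0.5 older; 20% young | 1.00 | 0.99 / 0.99 | 0.864 / 0.861 | 0.06 |
| Effect 6.0 young, 0.5 older; extra 3 mmHg age gap in both arms; 30% young | 2.15 | 2.16 / 2.15 | 0.894 / 0.866 | 0.18 |

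Neither model is biased.

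**2. Precision.** Let p be the share of younger men, g the age gap in mean change pooled over arms, and SD the residual SD without age. Then SE(with) / SE(without) = √(1 − p(1−p)g²/SD²).

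- SD 10, p = 0.20, g = 2: p(1−p)g²/SD² = 0.16 × 4/100 = 0.0064. SE without age = 10 × √(2/272) = 0.857; with age, 0.855. The CI half-width goes from 1.681 to 1.675 mmHg, a fall of 0.3%.
- SD 8–12, p = 10–50%, g = 1–3: the SE falls by 0.03% to 1.8%.
- g = 5, an extreme value: 0.8% to 5.0%.

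**3. Within-arm LS means.** Suppose there are two age groups and LS means weight factor levels equally. This is a common default, but the protocol does not state it. The MMRM then gives younger men weight 0.5, while the ANCOVA without age gives them their observed share p. The shift is (0.5 − p) × g:

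| | g = 2 mmHg | g = 4 mmHg |
|---|---|---|
| p = 0.15 | 0.7 | 1.4 |
| p = 0.30 | 0.4 | 0.8 |

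The model has one age coefficient for both arms, so the shift is the same in each and cancels from the treatment difference. It does not cancel from the within-arm means, which are the only output named for the MMRM.

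**4. What a main effect cannot show.** If the drug effect were 3 mmHg in younger and 1 mmHg in older men (assumed), the average would be 3p + (1 − p), which is 1.3 mmHg at p = 0.15 and 1.6 at p = 0.30. Adding age group as a main effect leaves that average essentially unchanged. Only estimates by age group would show the difference. They would be imprecise: with p = 0.20 and SD 10, about 54 younger men per arm give a half-width of 1.96 × 10 × √(2/54.4) = 3.8 mmHg.

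**The case against.** The strongest reply is that nothing is broken. The ANCOVA contains the stratification factor and the baseline value, no test is planned, and the SE hardly moves. Age group is not used everywhere either: the stratified rank ANCOVA for incontinence in 7.4.2 also omits it. A sensitivity analysis may legitimately change more than one feature. The safety reading also rests on threshold counts, JNC-7 shifts and rule-based hypertension events, not on one mean. Further subgroup tables are normally left to the SAP. All of this stands, and it limits the point to a minor one.

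The age evidence is also softer than it looks. The protocol never defines its age groups, so a cut at 55 cannot be assumed. It does not define young subjects in the statements on blood pressure and pulse; in the pharmacokinetic comparison, younger means 18 to 45, while this trial enrols from 40. Section 1.3.1 also reports no overall safety difference between patients under 65 and those 65 or older.

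A reader might infer that the two models are not comparable, that the ANCOVA is biased, or that worthwhile precision is lost. Steps 1 and 2 of the working rule these out. A reader might also infer that adding age group would reveal a larger drug effect in younger men. It would not, because the reported finding concerns rises on treatment, which is possible effect modification.

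What the reply does not answer is why two models for the same outcome, set out in consecutive paragraphs as main and sensitivity analysis, have different covariates. The terms are written into the protocol, so this is not detail left to the SAP.

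**Conclusion.** The mismatch is real, unexplained and minor. The main ANCOVA is valid and unbiased for the average treatment difference, and the SE cost is at most about 2% for age gaps up to 3 mmHg. The consequence is interpretive: a difference between the ANCOVA and the MMRM cannot be assigned to missing data alone. In within-arm LS means, the covariate list by itself could account for 0.4 to 1.4 mmHg, against a reported drug effect of about 1 mmHg. That range assumes two equally weighted age groups, 15–30% younger men and a 2–4 mmHg age gap, none of which the protocol states. The documents do not establish that men aged 40 to 54 have the larger rise. They do give enough reason to display the treatment difference by age.

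**What to change.** In section 7.5.3, add age group as a fixed factor to the vital-sign ANCOVA, so that both vital-sign models use the same covariates and match the efficacy ANCOVA. If the sponsor prefers to keep the difference, state the reason.

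Also show the LS mean treatment difference with 95% CI by the age groups used in the model, for office and home measurements separately, as description and without p-values. Section 7.4.1.3 already plans age subgroups for the primary endpoint, so the same grouping can be used.

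The cost is one model term and one table, with no new data. The change can be carried into the SAP, which section 7 requires to be final before database softlock.
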